3.1 Visit Schedule and Visit Windows

Assessments and study visits will be performed as listed in Table 1. Paragraph no. 7 “Assessments and procedures” of Study Protocol contains additional details about scheduled visits, evaluations and assessments that are performed during the study.

Baseline is defined as the last visit prior to randomization. Unless otherwise specified, baseline values are defined as the measurements taken during this visit.

Table 1: Schedule of evaluations

Study procedures	Screening	Baseline	Day 1	Day 2	Week 1	End of treatment	End of follow up
Informed Consent	X						
Inclusion/Exclusion Criteria	X	X					
Pregnancy Test	X						X
Randomization		X					
Demographics	X						
Medical History	X						
Previous And Concomitant Medications	X	X	X	X	X	X	X
Clinical severity score	X	X	X	X	X	X	X
Liker scale	X	X	X	X	X	X	X
Dyspnea VAS scale	X	X	X	X	X	X	X
Body temperature	X	X	X	X	X	X	X
Hematology evaluations*	X	X	X	X	X	X	X
Oxygen treatment (time and quantity)	X	X	X	X	X	X	X
Mechanical ventilation (Yes/No)	X	X	X	X	X	X	X
ICU admission (Yes/no)	X	X	X	X	X	X	X
Chest radiologic imaging	X	X§	X§	X§	X§	X	X§
PaO ₂ , SpO ₂ , FiO ₂	X	X	X	X	X	X	X
CRP, Hs-CRP	X	X	X	X	X	X	X
Cytokine profile **	X	X	X	X	X	X	X
Reparixin blood concentration **			X	X	X	X	X
SARS-CoV-2 virologic counts **		X			X	X	X
Study drug dispensation		X					
Verify study medication dosing compliance			X	X	X	X	
Record AEs / SAEs	X	X	X	X	X	X	X

* Including routine hematology as for local laboratory procedures and predefined hematochemical evaluations required for this study;

** Not mandatory; § When deemed appropriate by the investigators.

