5.8 Other baseline characteristics

The following information at baseline will be descriptively reported by means summary statistics:

- Clinical severity score (categorical)
- Dyspnea VAS scale (continuous)
- Respiratory parameters (continuous)
 - FiO₂ (%)
 - Respiration rate (Breath/min)
 - PaO₂ (mmHg)
 - SpO₂ (%)
 - PaO₂/FiO₂ (Ratio)
 - Acute Respiratory Distress Syndrome (ARDS) severity and their categorical evaluation, if applicable.
- Additional information
 - Did the subject experience any Adverse Events? (yes, no);
 - Has the subject been admitted to the ICU? (yes, no);
 - Was oxygen administered to the subject? (yes, no);
 - Has the subject been mechanically ventilated? (yes, no).

6. Evaluation of Treatment Compliance and Exposure

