7.2.2 Comparison between treatments

Along with the above summary statistics, comparisons between treatments will be performed as detailed in the next sub-sections. Parametric test (i.e. two-sample t-test for continuous variables, Chi-square test for categorical) will be adopted as first choice. In case the required assumptions are not met, the corresponding non-parametric counterpart will be used (i.e. the two-sample Mann–Whitney U test for continuous variables, and the Fisher’s Exact test for the categorical). Normality of continuous data is assessed by Kolmogorov-Smirnov test.

Comparison will be performed at each available time point, where applicable. Any exception will be declared.

7.2.2.1 *Composite endpoint of phase 2 using Oxygen Delivery System Classification*

The composite endpoints will be summarized along with their single component by a binomial response rate at each time point (only the first event will be considered). The Clopper-Pearson method will be used to estimate the two-sided 95% CIs.

Time to composite endpoint(s) will be performed using the KM methodology and the one-sided log-rank test will be used to test for differences between treatment groups.

7.2.2.2 *Changes in clinical severity score*

Number and proportion along with the 95% confidence interval (Clopper-Pearson’s formula) of subjects with a clinical severity score improvement of at least two points compared to randomization or live discharge from the hospital will be calculated and compared.

7.2.2.3 *Dyspnea severity (Liker scale and VAS scale)*

The comparison of the Liker scale between the two study treatment arms will be performed by means of Wilcoxon signed-rank test, given its ordinal nature.

Number and proportion along with the 95% confidence interval (Clopper-Pearson’s formula) of subjects with

any improvement (improved vs not-improved) will be calculated and compared.

VAS scale comparison between treatments will be performed according to its continuous nature.

7.2.2.4 *Changes in body temperature*

Comparison between treatments in change from baseline of the body temperature will be performed according to the continuous nature of the variable.

7.2.2.5 *Incidence of supplemental oxygen treatment*

Number and proportion along with the 95% confidence interval (Clopper-Pearson's formula) of subjects who worsened according to PaO₂/FiO₂ and to Oxygen Delivery System Classification based on oxygen support will be calculated and compared.

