At each time point the number and proportion of patients within each class (Severe, Moderate, or Mild for PaO₂/FiO₂; Invasive, High Flow, or Low Flow for the type of support) will be provided.

Finally, summary of cumulative quantity (L) and cumulative duration (hours) of oxygen treatment will be performed at 7 days and subsequent time points considering the variable as continuous.

7.2.2.6 *Incidence and duration of mechanical ventilation use*

Number and proportion along with the 95% confidence interval (Clopper-Pearson's formula) of subjects requiring mechanical ventilation will be calculated and compared.

Comparison between treatments in cumulative duration (hours) of mechanical ventilation will be performed at 7 days and subsequent time points considering the variable as continuous. Analysis will be performed overall and stratified by Invasive/Non-invasive mechanical ventilation.

7.2.2.7 *Incidence of ICU admission need*

Number and proportion along with the 95% confidence interval (Clopper-Pearson's formula) of subjects requiring ICU admission will be calculated and compared.

Comparison between treatments in duration (days) of ICU stay will be performed considering the variable as continuous.

7.2.2.8 *Change from baseline in lung damage extension and lung exudation degree (assessed by Chest CT or Rx)*

The comparison of the clinical evaluation of lung damage extension and lung exudation between the two study treatment arms will be performed by means of Wilcoxon signed-rank test.

7.2.2.9 *Respiratory parameters*

Change from baseline of FiO₂, Respiration rate, PaO₂, SpO₂ and PaO₂/FiO₂ will be compared between treatments considering the continuous nature of these variables.

7.2.2.10 *CRP and Hs-CRP*

CRP (mg/L) and Hs-CRP (mg/L) will be compared between treatments considering their continuous nature.

7.3 **Analysis of exploratory efficacy endpoints**

Explorative endpoints (section 3.5.3) will be analyzed at each available time points by means of descriptive statistics. Specifically, analyses will be provided for baseline visit, each post-baseline visit, and the change from baseline measurements to each visit. Comparison between treatments will be performed by means of two-sample t-test or, if assumptions of normality is not confirmed (by Kolmogorov-Smirnov test), two-sample Mann-Whitney U test.

In case of different units of measure considered for the same laboratory parameter, all values will be converted

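### Nine continuous secondary variables with a planned baseline value are compared without adjusting for it, which gives up precision that ANCOVA would recover at almost no cost

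*SAP*

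**What the plan says.** SAP 7.2.2 sets the general rule: "Parametric test (i.e. two-sample t-test for continuous variables, Chi-square test for categorical) will be adopted as first choice". It continues: "In case the required assumptions are not met, the corresponding non-parametric counterpart will be used", which for continuous data is the Mann-Whitney U test. Neither test takes a covariate. The sub-sections then give the form of each outcome:

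- **Temperature (7.2.2.4):** "Comparison between treatments in change from baseline of the body temperature will be performed according to the continuous nature of the variable".
- **FiO2, respiration rate, PaO2, SpO2, PaO2/FiO2 (7.2.2.9):** change from baseline; the changes "will be compared between treatments considering the continuous nature of these variables".
- **CRP and Hs-CRP (7.2.2.10):** these "will be compared between treatments considering their continuous nature"; neither change nor baseline is mentioned.
- **Dyspnea VAS (7.2.2.3):** "VAS scale comparison between treatments will be performed according to its continuous nature"; whether the value or its change is tested is left open.

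The baseline data are planned. SAP 3.1 states: "Baseline is defined as the last visit prior to randomization". Table 1 there schedules VAS, temperature, PaO2, SpO2, FiO2, CRP and Hs-CRP at the baseline visit, and SAP 5.8 lists baseline respiration rate and PaO2/FiO2. Among the efficacy analyses, baseline covariates appear only in the regression sensitivity models for the primary endpoints (7.1.3) and the subgroup interaction models (4.4).

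**The concern.** When an outcome is measured before and after randomization, a change score fixes the baseline coefficient at 1 and a raw-value comparison fixes it at 0. ANCOVA estimates it, and unless the true coefficient is close to the fixed one the estimated version is more precise.

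Phase 2 has only 16 controls, and randomization is stratified by site but not by severity. Eligibility spans PaO2/FiO2 from above 100 to below 300, and a raised CRP is only one of several alternative inflammation criteria, so baselines may vary widely. SAP 7.1.3.1 already provides for chance imbalance in the primary endpoint's sensitivity model, but the continuous secondary endpoints have no counterpart. At stake is the sharpness of the phase 2 description of oxygenation, inflammation and dyspnea, and of any subgroup repeats under SAP 4.4, where the arms are smaller still.

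**Working it through.** **The plan's own figure.** The documents give no effect size, SD or power for any continuous secondary endpoint. The only phase 2 design figure is the approximately 80% power for the composite in SAP 3.2. With 46 events, 2:1 allocation and medians of 2 and 5 days (HR 0.40), sqrt(46 × 2/9) × ln(2.5) − 1.96 = 3.197 × 0.916 − 1.96 = 0.97, or 83.4% for a fixed design. Simulation with the Table 4 efficacy and futility boundaries gives 80.1%. The stated figure reproduces, and the point here does not depend on it.

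**Inputs from the documents.** 48 patients, 32 on reparixin (Protocol 1), so 16 controls; two-sided 0.05 for secondary comparisons (SAP 4.1).

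**Assumptions.** Equal baseline and post-baseline SD, σ; baseline to post-baseline correlation ρ of 0.3, 0.5 or 0.7; all 48 values observed; for power, a true difference of 0.8σ.

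**Variance of the treatment difference**, in units of σ²(1/32 + 1/16):

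- raw value: 1
- change score: 2(1 − ρ)
- ANCOVA: (1 − ρ²) × (1 + 1/(48 − 4)) = (1 − ρ²) × 1.0227

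| | ρ = 0.3 | ρ = 0.5 | ρ = 0.7 |
|---|---|---|---|
| Change score | 1.40 | 1.00 | 0.60 |
| ANCOVA | 0.931 | 0.767 | 0.522 |
| ANCOVA / change | 0.665 | 0.767 | 0.869 |
| ANCOVA / raw | 0.931 | 0.767 | 0.522 |
| Power, raw (simulated) | 72.6% | 72.3% | 72.8% |
| Power, change (simulated) | 58.1% | 72.5% | 90.8% |
| Power, ANCOVA (simulated) | 75.6% | 83.2% | 94.2% |

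The power rows come from 40,000 simulated trials per correlation, using t tests. At ρ = 0.5, 1/0.767 = 1.30, so adjustment is worth about 30% more patients.

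**Where the gain stops.** Against raw values, ANCOVA wins when (1 − ρ²) × 45/44 < 1, that is ρ > sqrt(1/45) = 0.149. At ρ = 0 it costs about 2% of variance. Against change, it wins when (1 + ρ)/2 × 45/44 < 1, that is ρ < 88/45 − 1 = 0.956.

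**Unequal SDs.** If the post-baseline SD is k times the baseline SD, the large-sample ratio of ANCOVA to change is k²(1 − ρ²)/(k² + 1 − 2ρk).

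- k = 1.5, ρ = 0.7: 1.1475/1.15 = 0.998, or 0.998 × 1.0227 = 1.02 at N = 48. The gain is gone.
- k = 0.7, ρ = 0.5: 0.3675/0.79 = 0.465. The gain is large.

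The ratio to a raw-value comparison does not depend on k.

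**Realised imbalance.** The standard error of the baseline mean difference is sqrt(1/32 + 1/16) = 0.31σ. With equal SDs, an imbalance of that size enters a raw-value comparison with weight ρ and a change-score comparison with weight ρ − 1. At ρ = 0.5 this shifts the estimate by about 0.15σ, in opposite directions. ANCOVA removes the shift on average.

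**The case against.** The planned tests are legitimate. Protocol 9.4.2.5 calls for parametric tests with non-parametric counterparts, and the SAP follows it. These are secondary tests at a nominal 0.05, repeated at each time point with no multiplicity control described. The correlations and SDs above are assumed. The t-test is only the first choice, and if Mann-Whitney is used for a skewed variable such as CRP, the variance ratios do not carry over directly. All of this stands and limits the weight of the point.

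A reader might also infer more than the documents support:

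- **Bias.** Over repeated randomization, both the raw-value and the change-score comparisons are unbiased and keep their type I error. The shift computed above is conditional on a particular imbalance and only part of that imbalance reaches the estimate.
- **Influence on phase 3.** SAP 7.1.3.1 rests the decision to proceed on the primary analysis alone. Table 6 refers generally to phase 2 results and ties no trigger to any of these tests, so any influence is indirect.
- **Wider confidence intervals.** SAP 7.2.2 names intervals only for proportions and plans none for a continuous treatment difference.

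What remains is that the covariate is already planned for each of the nine variables, and the unadjusted fallback ignores it just as the t-test does.

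**Conclusion.** The point holds as a loss of precision in named secondary endpoints. Under the stated assumptions at 32 versus 16, baseline adjustment would cut variance by about 13% to 34% against change scores and 7% to 48% against raw values. These ranges rest on equal SDs and correlations between 0.3 and 0.7. The comparison with change is the less secure, because it depends on the SD ratio.

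Two extensions should be resisted. It is not true that every continuous secondary variable has a baseline: oxygen quantity and duration and ventilation duration accumulate from randomization, and ICU stay is discharge minus admission. Nor is adjustment strictly free, given the degree of freedom it uses. For VAS, the documents support only that the form is unstated, not that raw values are tested.

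**What to change.** Before database lock, amend SAP 7.2.2 for VAS, temperature, FiO2, respiration rate, PaO2, SpO2, PaO2/FiO2, CRP and Hs-CRP:

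1. At each post-baseline visit, compare treatments by ANCOVA of the post-baseline value on treatment and baseline value, with CRP and Hs-CRP on the log scale. This also settles the unstated form for VAS.
2. Make rank-based ANCOVA the fallback in place of Mann-Whitney.
3. Report the adjusted difference with its 95% CI.
4. Keep the descriptive change-from-baseline tables of 7.2.1.
5. Leave oxygen quantity and duration, ventilation duration and ICU stay as they are.

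The cost is SAP wording and one degree of freedom. No new data are needed. Protocol 9.4.2.5 leaves the details to the SAP and allows transformation, so the change fits within it. It does not deal with values missing after death or discharge: SAP 4.8 summarises observed values only, and that needs separate treatment.

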8.1 Adverse events

Any AE which starts at or after the first administration of study treatment will be considered a Treatment Emergent Adverse Event (TEAE). Pre-treatment AEs and TEAEs will be presented separately. Pre-treatment AEs will be presented in the listings only. In case of missing or incomplete dates not allowing a direct allocation to any of the two categories of AEs, a worst-case allocation will be done according to the available parts of the onset and the end dates (see Table 8). The AE will be allocated to the first category allowed by the available data, according to the following order:

- TEAE;
- Pre-treatment AE.

All AEs will be assigned to a PT and will be classified by primary SOC according to the MedDRA thesaurus. In addition, each AE will be graded according to severity definitions as “Mild”, “Moderate” or “Severe”.

TEAEs will be reported on a per-subject basis, i.e. if a subject reported the same event repeatedly (i.e. events mapped to the PT) the event will be counted only once.

For summaries, the drug-event relationship will be assessed as “None”, “Unlikely”, “Possible” “Probable” or “Highly probable”. Any TEAE reported in the study having a possible, probable or highly probable relationship to IMP will be defined as “Adverse Drug Reaction” (ADR).

The following tables and listings will be presented by treatment group:

- An overview of TEAEs including the number of subjects who exhibited at least one TEAE, at least one severe TEAE, at least one serious TEAE, at least one non-serious TEAE, at least one ADR, at least one serious ADR, number of TEAEs, number of non-serious TEAEs, number of TESAEs, number of ADRs, number of serious ADRs, number of deaths, number of subjects who temporarily interrupted IMP due to a TEAE, number of subjects who permanently interrupted IMP due to a TEAE;
- Summary of TEAEs by primary SOC and PT;
- Summary of TEAEs by primary SOC, PT and Severity;
- Summary of Serious TEAEs by Primary SOC and PT;
- Summary of ADRs by Primary SOC and PT;
- Summary of ADRs by Primary SOC and PT and Severity;
- Summary of TEAEs leading to IMP temporary interruption by Primary SOC and PT;
- Summary of TEAEs leading to IMP permanently interruption by Primary SOC and PT;
- Summary of TEAEs leading to Death by Primary SOC and PT;
- Listing of all AEs by Subject;
- Listing of SAEs by Subject;
- Listing of ADR by Subject;
- Listing of Deaths.

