## **Adverse Drug Reaction**

An **Adverse Drug Reaction (ADR)** is defined as an adverse experience which is a reasonably likely to have been caused by the drug. Adverse events are to be considered unsuspected if the relationship to the study drug as described in the table in section 7.3.4 is none or unlikely; whereas any AE reported in the study having a possible, probable or highly probable relationship to study drug will be considered as an ADR. The definition covers also medication errors and uses outside what is foreseen in the protocol, including misuse and abuse of the product.

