## 7.3.3 RECORDING

AEs will be collected and recorded for any untoward event that occurs in a patient from the time he or she signs the Informed Consent for the trial until the end of the follow up period. Thus, any untoward medical occurrences or unfavorable and unintended signs, symptoms, or diseases that occur in the pretreatment, in treatment, or post treatment period are to be considered AEs and/or SAEs, and consequently recorded and reported as such. Should a non-serious AE become serious, the Investigator will then follow the same reporting procedures as for SAEs.

Each AE will be described by:

- Its duration (start and stop dates).
- Its seriousness.
- Its relationship to the study drug (suspected/unsuspected).
- Action(s) taken.
- Outcome.

Medical conditions/diseases and related signs/symptoms present before starting study treatment shall be documented in the medical history section of the CRF; these conditions are considered AEs only if they increase either in frequency or severity once informed consent has been signed.

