9.2 Partial date conventions

Table 8: Algorithm for Treatment Emergence of Adverse Events

START DATE	STOP DATE	ACTION
Known	Known, Partial or Missing	If start date < IMP start date, then not TEAE If start date >= IMP start date, then TEAE
Partial, but known components show that it cannot be on or after IMP start date	Known, Partial or Missing	Not TEAE
Partial or Missing	Known	If stop date < IMP start date, then not TEAE If stop date >= IMP start date, then TEAE
	Partial	Impute stop date as latest possible date (i.e. last day of month if day unknown or 31st December if day and month are unknown), then: If stop date < IMP start date, then not TEAE If stop date >= IMP start date, then TEAE
	Missing	Assumed TEAE

Table 9: Algorithm for Prior/Concomitant medications

START DATE	STOP DATE	ACTION
Known	Known	
If stop date < date of informed consent, assign as prior
 
If stop date >= date of informed consent and start date <= end of treatment, assign as concomitant
 
If stop date >= date of informed consent and start date > end of treatment, assign as post study

	Partial	
Impute stop date as latest possible date (i.e. last day of month if day unknown or 31st December if day and month are unknown), then:
 
If stop date < date of informed consent, assign as prior
 
If stop date >= date of informed consent and start date <= end of treatment, assign as concomitant
 
If stop date >= date of informed consent and start date > end of treatment, assign as post treatment

	Missing	
If stop date is missing could never be assumed a prior medication
 
If start date <= end of treatment, assign as concomitant
 
If start date > end of treatment, assign as post treatment

Partial	Known	
Impute start date as earliest possible date (i.e. first day of month if day unknown or 1st January if day and month are unknown), then:
 
If stop date < date of informed consent, assign as prior
 
If stop date >= date of informed consent and start date <= end of treatment, assign as concomitant
 
If stop date >= date of informed consent date and start date > end of treatment, assign as post treatment

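### The SAP has no worsening clause for adverse events with a known pre-dose onset, and it tabulates only treatment-emergent serious events where the protocol promises all SAEs by arm (minor)

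*SAP*

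**What the plan says.** **TEAE rule.** SAP 8.1: "Any AE which starts at or after the first administration of study treatment will be considered a Treatment Emergent Adverse Event (TEAE". There is no clause for worsening or for becoming serious.

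**Date algorithm (SAP 9.2, Table 8).** For a known start date: "If start date < IMP start date, then not TEAE". The second case, "Partial, but known components show that it cannot be on or after IMP start date", has the same result. Neither looks at the stop date or at later severity.

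**Where the excluded events go.** SAP 8.1: "Pre-treatment AEs will be presented in the listings only".

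**Serious events.** The only SOC/PT table for them is "Summary of Serious TEAEs by Primary SOC and PT". Protocol 9.4.3 names TEAEs, ADRs and SAEs side by side, to be shown by arm, SOC and PT, and restricts only the first to treatment-emergent events. SAP 3.6 still lists AEs and SAEs over the whole study, and SAP 4.9 reports no change to the planned analysis.

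**Drug reactions.** The SAP starts from TEAEs: "Any TEAE reported in the study having a possible, probable or highly probable relationship to IMP will be defined as" an ADR. Protocol 7.3.1 starts from all AEs: "any AE reported in the study having a possible, probable or highly probable relationship to study drug will be considered as an ADR".

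**Recording.** Under Protocol 7.3.3, AEs are collected from consent, and an event may change status: "Should a non-serious AE become serious, the Investigator will then follow the same reporting procedures as for SAEs". Protocol 7.3.4 asks for one severity grade per episode, the highest reached.

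**The concern.** AEs are recorded at two visits before treatment (Screening and Baseline, SAP Table 1), so pre-dose onsets are expected. In patients hospitalized with severe COVID-19 pneumonia, an event that starts between consent and first dose may well get worse afterwards. If it stays one record with its pre-dose onset date, the SAP never tabulates it by SOC and PT. If it is fatal, it raises the overview's death count but is missing from the SOC/PT table of TEAEs leading to death, so the two would disagree with no explanation.

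At stake is the tabulated incidence of serious and of drug-related events, which could be too low by the patients concerned. A reader comparing the report with Protocol 9.4.3 would also look for an all-SAE table by arm and find neither the table nor a statement that it was dropped.

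**Working it through.** The plan gives no figure to reproduce. The check is a count of outputs, a run through Table 8, and the weight of one patient.

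**1. SOC/PT tables in SAP 8.1.** TEAEs; TEAEs by severity; serious TEAEs; ADRs; ADRs by severity; TEAEs leading to temporary interruption; to permanent interruption; to death. Total 8. All are limited to TEAEs, or to ADRs that the SAP defines as a subset of TEAEs.

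**2. Overview counts in SAP 8.1.** Six subject counts (TEAE, severe, serious, non-serious, ADR, serious ADR), five event counts (TEAEs, non-serious, serious, ADRs, serious ADRs), deaths, and two interruption counts: 6 + 5 + 1 + 2 = 14. Only deaths is free of the limit, so 13 of 14 carry it.

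**3. Listings.** All AEs, SAEs, ADRs, deaths: 4, of which only the ADR listing is limited to TEAEs.

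**4. Table 8.** There are five date cases. Two exclude a pre-dose onset regardless of later course (start known; start partial but certainly pre-dose). The other three (start partial or missing, with stop known, partial or missing) use the stop date or default to TEAE. Setting first dose at day 0, for an event that becomes serious on day 3:

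| Start | Stop | Table 8 result |
|---|---|---|
| Day -1 | Day 6 | Not TEAE |
| Missing | Day 6 | TEAE |
| Missing | Missing | TEAE |

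The first event appears in 0 of 8 tables.

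**5. Protocol against SAP for serious events.** Protocol 9.4.3: SAEs by arm, SOC and PT, no treatment-emergent limit. SAP 8.1: serious TEAEs only. SAP 4.9: no change; its one clarification concerns supplemental oxygen.

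**6. Weight of one patient.** At 2:1, 48 = 32 + 16 and 111 = 74 + 37. One affected patient moves a given row by at most 100/n points, and by nothing if that patient already has another event in the row. The documents give no rate for such events. The range of 0 to 2 patients per arm is an assumption for illustration.

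| Arm | n | 1 patient | 0 to 2 patients |
|---|---|---|---|
| Phase 2 reparixin | 32 | 3.1 | 0 to 6.3 |
| Phase 2 control | 16 | 6.3 | 0 to 12.5 |
| All 111, reparixin | 74 | 1.4 | 0 to 2.7 |
| All 111, control | 37 | 2.7 | 0 to 5.4 |

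**The case against.** **Sites may record the worsening as a new AE.** Protocol 7.3.3 sends conditions present before study treatment to medical history and makes them AEs only on an increase in frequency or severity. If the AE is dated from that increase, an on-treatment aggravation is already a TEAE. This stands in part. But 7.3.3 gives no onset-date rule, also calls pre-treatment occurrences AEs, and describes one event becoming serious. The single highest grade per episode in 7.3.4 points to one record. The CRF would settle it and is not available.

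**The event is not hidden.** A reader might infer that it can be seen only in by-subject listings. The documents do not support that. Deaths are counted without a TEAE limit, SAP 5.3 summarizes reasons for stopping study drug, and SAP 7.2.2.5 to 7.2.2.7, 8.2 and 8.3 summarize oxygenation, ventilation, ICU, laboratory values and vital signs by arm. The DMC reviews in SAP 4.6 cover AEs without a TEAE limit. What is missing is the direct tabulation by SOC and PT.

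**TEAE status does not always rest on onset date alone.** It does so in only two of the five date cases. Counting an event with a missing onset as a TEAE is the worst-case allocation that SAP 8.1 announces, not an error.

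**The ADR difference is largely nominal.** A drug cannot cause an event that began before its first dose. Only a related aggravation could differ, which is the same gap again.

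**The any-AE promise is arguable.** Protocol section 3 names patients with any AE beside TEAEs, but 9.4.3 lists no all-AE table. The SAE table is the firm difference.

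**The counts repeat one rule.** The 8 and the 13 describe reach, not 21 separate faults. Protocol 8.2 does not allow temporary discontinuation, so one of the tables should be empty anyway. The control-arm figures also presuppose a first-administration date for standard of care, which the SAP does not define.

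**Conclusion.** Two things hold. The SAP's rule excludes a known pre-dose event from every SOC/PT table even if it worsens or becomes serious on treatment under the same record. The SAP also narrows the protocol's SAE summary to treatment-emergent events without declaring it. The second holds on the text even if no patient is ever affected. The first has an effect only if sites keep one record with the pre-dose onset.

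The number of patients is unknown and may be zero. Each one costs a row at most 3.1 points on reparixin or 6.3 on control in phase 2. A reader might infer that the comparison of arms is biased or that SAE reporting is weakened. Neither is shown: the same rule is written for both arms, and reporting under Protocol 7.3.6 and 7.3.7 does not depend on TEAE status. No efficacy decision depends on the rule. Severity: minor.

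**What to change.** 1. Add to SAP 8.1 and to the first two date cases of Table 8: *An AE that starts before first administration is also a TEAE if it increases in severity or becomes serious on or after first administration.* Apply it where the change can be dated. Protocol 7.3.3 lists no worsening date among the AE fields, so the clause will work mainly for seriousness. There, the first SAE form, due within 24 hours of the investigator learning of the event (Protocol 7.3.6), gives an approximate date. Flag undatable cases in the listings and do not reclassify them.
2. Add a by-arm summary of all SAEs from consent, by SOC and PT, and optionally one of all AEs. If the sponsor prefers TEAE-only tables, declare the restriction in SAP 4.9 as a change from Protocol 9.4.3.
3. Leave the ADR definition alone. Under item 1, a datable, related on-treatment aggravation becomes a TEAE and so an ADR.

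Cost: a sentence of SAP wording, one or two extra tables, a listing flag, and a slightly higher TEAE count. The added tables need no new data.
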